In a short-term (9 week) study, non-demented elderly patients (aged 66 to 89 years) with MDD, quetiapine XR dosed flexibly in the range of 50 to 300 mg/day demonstrated superior efficacy to placebo in reducing depressive symptoms as measured by improvement in MADRS total score (LS mean change vs placebo -7.54). In this study, patients randomized to quetiapine XR received 50 mg/day on Days 1-3, the dose could be increased to 100 mg/day on Day 4, 150 mg/day on Day 8, and up to 300 mg/day depending on clinical response and tolerability. The mean dose was 160 mg/day. Other than the incidence of extrapyramidal symptoms, the tolerability of quetiapine XR once daily in elderly patients was comparable to that seen in adults (aged 18 to 65 years). The proportion of randomized patients over 75 years of age was 19%.

Clinical Safety

Higher rates of extrapyramidal symptoms were seen in quetiapine treated patients compared to those treated with placebo in short-term, placebo-controlled clinical trials in MDD and bipolar depression. In short-term, placebo-controlled monotherapy clinical trials in MDD, the aggregated incidence of extrapyramidal symptoms was 5.4% for quetiapine XR and 3.2% for placebo. In a short-term placebo-controlled monotherapy trial in elderly patients with MDD, the aggregated incidence of extrapyramidal symptoms was 9.0% for quetiapine XR and 2.3% for placebo. In both bipolar depression and MDD, the incidence of the individual AEs (eg, akathisia, extrapyramidal disorder, tremor, dyskinesia, dystonia, restlessness, muscle contractions involuntary, psychomotor hyperactivity, and muscle rigidity) did not exceed 4% in any treatment group.

Suicide

Physicians should consider the potential risk of suicide-related events after abrupt cessation of quetiapine treatment, due to the known risk factors for the disease being treated.

Other psychiatric conditions for which quetiapine is prescribed can also be associated with an increased risk of suicide-related events. In addition, these conditions may be comorbid with major depressive episodes.

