Patients with a history of suicide-related events, or those exhibiting a significant degree of suicidal ideation prior to commencement of treatment are known to be at greater risk of suicidal thoughts or suicide attempts and should receive careful monitoring during treatment. A meta-analysis of placebo-controlled clinical trials of AD drugs in adult patients with psychiatric disorders showed an increased risk of suicidal behavior with ADs compared to placebo in patients less than 25 years old.

Close supervision of patients, in particular those at high risk, should accompany drug therapy, especially in early treatment and following dose changes. Suicidal risk monitoring will be performed in this study as described in Section 8.2.5.

In clinical studies of patients with MDD the incidence of suicide-related events observed in young adult patients (younger than 25 years of age) was 2.1% (3/144) for quetiapine and 1.3% (1/75) for placebo. A population-based retrospective study of quetiapine for the treatment of patients with MDD showed an increased risk of self-harm and suicide in patients aged 25 to 64 years without a history of self-harm during use of quetiapine with other ADs.

Adverse Drug Reactions

The most commonly reported adverse drug reactions with quetiapine ($\geq 10\%$) are somnolence, dizziness, headache, dry mouth, withdrawal (discontinuation) symptoms, elevations in serum triglyceride levels, elevations in total cholesterol (predominantly low-density lipoprotein cholesterol), decreases in high-density lipoprotein cholesterol, weight gain, decreased hemoglobin, and extrapyramidal symptoms.

Overdose

In general, reported signs and symptoms were those resulting from an exaggeration of the active substance's known pharmacological effects; ie, drowsiness and sedation, tachycardia, hypotension, and anti-cholinergic effects.

Overdose could lead to QT-prolongation, seizures, status epilepticus, rhabdomyolysis, respiratory depression, urinary retention, confusion, delirium and/or agitation, coma, and death. Patients with pre-existing severe cardiovascular disease may be at an increased risk of the effects of overdose.

For further information regarding the comparator refer to the Summary of Product Characteristics (SmPC)²⁸ (or local equivalent, if applicable).

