5.7.2. Adverse Events

The verbatim terms used in the CRF by investigators to identify adverse events will be coded using the Medical Dictionary for Regulatory Activities (MedDRA). All AEs and special reporting situations, whether serious or non-serious, will be reported from the time a signed and dated ICF is obtained until completion of the participant's 2-week safety follow-up visit. Serious AEs, including those spontaneously reported to the investigator within 30 days after the last dose of study intervention, must be reported.

Any AE occurring at or after the initial administration of study intervention through completion of the participant's 2-week safety follow-up visit is considered to be treatment emergent. Serious AEs reported within 30 days after the last dose of study intervention are also regarded as treatment emergent. If the event occurs on the day of the initial administration of study intervention, and either event time or time of administration are missing, then the event will be assumed to be treatment emergent. If the event date is recorded as partial or completely missing, then the event will be considered to be treatment emergent unless it is known to be prior to the first administration of study intervention based on partial onset date or resolution date. All reported treatmentemergent adverse events will be included in the analysis. For each adverse event, the number and percentage of participants who experience at least 1 occurrence of the given event will be summarized by intervention group.

Summary tables, for the first 8 weeks and for the whole study, will be provided for treatmentemergent adverse events:

- AEs
- Serious AEs (SAEs)
- AEs leading to discontinuation of each study agent within a study intervention
- AEs by severity

- AEs by relationship to each study agent within a study intervention
- AEs leading to dose interruption/dose modification of each study agent within a study intervention.

In addition to the summary tables, listings will be provided for participants who:

- Had SAEs
- Had AEs leading to discontinuation of study intervention.

Incidence of treatment-emergent adverse events of special interest will be summarized, grouped in the following MedDRA-based categories: sedation, dissociation, suicidality, suggestive of abuse potential, cystitis, and hepatic impairment. See Appendix 8 for a list of adverse events in each category.

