6.8. Appendix 8 Adverse Events of Special Interest

Adverse events of special interest are defined and grouped in the following MedDRA based categories as follows:

Sedation: sedation; somnolence; altered state of consciousness; depressed level of consciousness; hypersomnia; stupor

Dissociation: depersonalisation/derealisation disorder; derealisation; dissociative disorder; flashback; hallucination; hallucination, auditory; hallucination, visual; hallucination, illusion; somatic hallucination; hyperacusis; tinnitus; diplopia; vision blurred; ocular discomfort; photophobia; visual impairment; dysesthesia; oral dysesthesia; paraesthesia; paraesthesia oral; pharyngeal paraesthesia; time perception altered; daydreaming; delusional perception; feeling hot; feeling cold; feeling of body temperature change

Suicidality: completed suicide; depression suicidal; intentional overdose; intentional self-injury; multiple drug overdose intentional; poisoning deliberate; self-injurious behavior; self-injurious ideation; suicidal behavior; suicidal ideation; suicide attempt; toxicity to various agents

Suggestive of abuse potential: aggression; confusional state; decreased activity; dependence; disorientation; dissociation; dissociative disorder; dizziness; drug abuse; drug abuser; drug dependence; drug use disorder; drug detoxification; drug diversion; drug rehabilitation; drug tolerance; drug tolerance increased; drug withdrawal convulsions; drug withdrawal headache; drug withdrawal syndrome; euphoric mood; feeling abnormal; feeling drunk; feeling of relaxation; hallucination, auditory; hallucination, gustatory; hallucination, olfactory; hallucination, synesthetic; hallucination, tactile; hallucination, visual; hallucinations, mixed; inappropriate affect; mental impairment; product tampering; psychomotor hyperactivity; psychotic disorder; rebound effect; somatic hallucination; somnolence; substance abuser; substance use disorder; substance-induced mood disorder; substance-induced psychotic disorder; thinking abnormal; withdrawal arrhythmia; withdrawal syndrome

Cystitis: allergic cystitis; chemical cystitis; cystitis; cystitis erosive; cystitis hemorrhagic; cystitis interstitial; cystitis noninfective; cystitis ulcer active; cystitis-like symptom; pollakiuria; dysuria; micturition urgency; nocturia

Hepatic impairment: cholestasis and jaundice of hepatic origin; hepatic failure; fibrosis and cirrhosis; other liver damage-related conditions

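### The special-interest adverse event set has no extrapyramidal category, so the comparator's extrapyramidal effect gets no participant-level total, overall or by age

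*SAP*

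**What the plan says.** Protocol Section 3 sets a secondary objective of comparing safety and tolerability between the arms. Its endpoint is intervention-emergent adverse events, with those of special interest named explicitly. SAP 5.7.2 summarizes the latter in six groups: "sedation, dissociation, suicidality, suggestive of abuse potential, cystitis, and hepatic impairment". SAP Appendix 8 gives the terms in each, following Protocol 8.3.7, and the same lists serve both arms. SAP 5.8.7 repeats special-interest events by subgroup, including age 18 to 64 and 65 or over.

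Protocol 2.2.4 says that the reactions reported most often with quetiapine, at 10% or more, "are somnolence, dizziness, headache, dry mouth, withdrawal (discontinuation) symptoms, elevations in serum triglyceride levels". That list goes on to lipid, weight and hemoglobin effects and ends with extrapyramidal symptoms. For short-term monotherapy trials in MDD it gives an aggregate of 5.4% against 3.2% on placebo. For the trial in elderly patients, "the aggregated incidence of extrapyramidal symptoms was 9.0% for quetiapine XR and 2.3% for placebo". It then lists nine individual events as examples, ending with "psychomotor hyperactivity, and muscle rigidity) did not exceed 4% in any treatment group".

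The abuse-potential list in Appendix 8 includes "psychomotor hyperactivity; psychotic disorder; rebound effect; somatic hallucination; somnolence; substance abuser", and also "dissociation; dissociative disorder; dizziness; drug abuse; drug abuser" and "drug withdrawal convulsions; drug withdrawal headache; drug withdrawal syndrome".

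**The concern.** The comparator has a known effect that the protocol itself can show only by pooling several event terms, and the plan for the comparative special-interest summary does not pool them. Eight of the nine terms belong to no group. The ninth, psychomotor hyperactivity, is counted under abuse potential and nowhere else.

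At stake is whether a reader of the report can see how many participants in each arm had any extrapyramidal event. The question matters most in the elderly: Protocol 2.2.4 makes extrapyramidal symptoms the one exception when it describes tolerability there as comparable to that in younger adults. The age subgroup tables would carry the six existing groups but no extrapyramidal total.

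A smaller matter concerns the abuse-potential group. It contains reactions that the protocol expects from each drug for reasons unrelated to abuse, so its total needs its component terms beside it.

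**Working it through.** The plan states no figure for this point, so the check is a term match followed by simple arithmetic.

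**1. Extrapyramidal terms (Protocol 2.2.4) against the six lists (SAP Appendix 8)**

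| Term | Group |
|---|---|
| tremor | none |
| akathisia | none |
| dystonia | none |
| dyskinesia | none |
| restlessness | none |
| muscle rigidity | none |
| involuntary muscle contractions | none |
| extrapyramidal disorder | none |
| psychomotor hyperactivity | abuse potential only |

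Eight of nine are in no group.

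**2. Expected size, if the cited rates carried over to 311 quetiapine participants**

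- All ages at the MDD monotherapy rate: 0.054 × 311 = 16.8, about 17. At the placebo rate: 0.032 × 311 = 10.0. Excess: 5.4 − 3.2 = 2.2 percentage points.
- At the elderly rate, if it applied to everyone: 0.090 × 311 = 28.0. At the placebo rate: 0.023 × 311 = 7.2. Excess: 9.0 − 2.3 = 6.7 points. The documents do not give the expected number of elderly participants, so this excess cannot be turned into a count for that subgroup.
- At the 10% floor of the general list of common reactions: 0.10 × 311 = 31.1.

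The range is therefore about 17 to 31 or more participants.

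**3. Why single rows do not give this number**

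If term *i* has incidence *p_i*, the proportion with at least one of the terms lies between max(*p_i*) and the smaller of 1 and Σ*p_i*. Where it lies depends on how many participants have more than one term, and separate rows do not show that.

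Assume that the aggregate came only from the nine terms and that nobody had two. The average per term would then be 5.4% / 9 = 0.6%, or 0.006 × 311 = 1.9 participants. At 9.0% it would be 9.0% / 9 = 1.0%, or 3.1 participants. Rows of that size are easily passed over.

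**4. The abuse-potential group, both arms**

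- Quetiapine: 3 of the 11 reactions named at 10% or more match it (somnolence, dizziness, withdrawal symptoms). Somnolence also sits in the Sedation list: "sedation; somnolence; altered state of consciousness; depressed level of consciousness; hypersomnia; stupor".
- Esketamine: 2 of the 11 reactions that Protocol 2.2.3.4 names at 10% or more match it (dissociation, dizziness).
- Each of these has the same documented floor, 0.10 × 311 = 31.1 participants. Either arm could reach 10% or more in this group through expected reactions alone, and the documents do not say which arm would be higher.

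**The case against.** The best defence is that nothing is lost. SAP 5.7.2 tabulates every treatment-emergent event by arm, for the first 8 weeks and the whole study, with further tables by severity, relationship, and discontinuation or dose change. Akathisia, tremor and the rest will be in those tables. That stands: the events are ungrouped, not missing. It does not supply the number of participants with any of them.

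It can also be said that the categories serve surveillance. The amendment summary attributes the abuse, cystitis and hepatic groups to the regulatory environment and company commitments, and no formal test is attached; Protocol 9.4.4 offers between-arm comparisons of adverse events only where appropriate. This limits the consequence. Even so, Section 3 makes special-interest events part of a comparative endpoint.

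The rates deserve caution. They come from monotherapy trials, while quetiapine here is add-on treatment, and the all-ages excess over placebo is only 2.2 points.

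A reader might go further and infer that the lists were built for esketamine, that quetiapine's commonest reactions and its extrapyramidal events are filed as abuse, and that an esketamine excess is thereby masked. The documents do not support this. They do not state that origin for the lists. Only 3 of 11 quetiapine reactions (in an unranked list) and 1 of 9 extrapyramidal terms match the abuse list. Esketamine's dissociation and dizziness are in it too, so the net direction is unknown. Nor does SAP 5.7.2 say that only a category total will be shown.

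**Conclusion.** The concern holds as a gap in grouping. The comparative special-interest summary has no extrapyramidal category, although the protocol names these symptoms as a common reaction to the comparator and can show them only in aggregate. On the protocol's own rates this concerns about 17 of 311 quetiapine participants, or 31 or more at the 10% floor. Both figures assume that rates from elsewhere carry over to this trial. The effect on single rows (about 2 to 3 participants per term) further assumes no overlap between terms and an aggregate made only of the nine.

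The abuse-potential total should not be read as a between-arm contrast in abuse, because it counts expected reactions of both drugs. That is a reason to show its components. It is not evidence that the safety tables as a whole mislead or that they favour one arm. No hypothesis test, primary or key secondary result, or capture of events is affected.

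**What to change.** 1. In SAP Appendix 8, add a seventh grouping, extrapyramidal symptoms, made of the nine terms in Protocol 2.2.4. Present it beside the Protocol 8.3.7 categories as the number and percentage of participants with at least one term, by arm and by the SAP 5.8.7 age groups, with the individual terms underneath. Psychomotor hyperactivity can stand in two groups, as somnolence already does.
2. Keep the abuse-potential category as defined and show its preferred terms by arm. Add a note that its total includes somnolence, dizziness and withdrawal terms expected with quetiapine, and dissociation and dizziness expected with esketamine. Do not substitute a shortened list as the version for comparing the arms. Removing somnolence, dizziness and the withdrawal terms while leaving dissociation in place would be a contestable choice of its own.
3. Record the added grouping in SAP Appendix 2, since it goes beyond the protocol's list, and settle it before the comparative tables are produced.

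The cost is a few table rows and one SAP grouping that the protocol does not contain. No new data are needed, as all events are coded in MedDRA. Because the protocol gives the nine terms as examples, the new total may not match the definition behind the cited aggregates exactly, and a footnote should say so.

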- Transient, primarily asymptomatic, increases in systolic and diastolic blood pressure (SBP and DBP) were observed following administration of esketamine nasal spray, with maximum mean changes typically observed within 40 minutes of dosing (consistent with peak plasma elevations) and mean blood pressure values returning to, or close to, predose values within the 1.5-hour postdose timepoint. The blood pressure elevations did not appreciably attenuate over time with continued administration. Few participants (<2% across studies/study phase) discontinued esketamine treatment due to increased blood pressure.
 - In clinical trials, increases in SBP and DBP over time were about 7 to 9 mm Hg in SBP and 4 to 6 mm Hg in DBP at 40 minutes post dose and 2 to 5 mm Hg in SBP and 1 to 3 mm Hg in DBP at 1.5 hours post dose in participants receiving esketamine nasal spray plus oral ADs. The frequency of markedly abnormal blood pressure elevations of SBP (≥40 mm Hg increase) ranged from 8% (<65 years) to 17% (≥65 years) and DBP (≥25 mm Hg increase) ranged from 13% (<65 years) to 14% (≥65 years) in participants receiving esketamine nasal spray plus oral AD. The incidence of increased SBP (≥180 mm Hg) was 3% and DBP (≥110 mm Hg) was 4%.

- In the short-term Phase 3 studies, treatment with esketamine in combination with a newly initiated SSRI/SNRI did not influence any aspect of cognition studied in adult participants with TRD and was not associated with any systematic changes in cognition in the elderly participants. In the long-term open-label safety study, overall group mean performance on multiple cognitive domains including visual learning and memory, as well as spatial memory/executive function, either improved or remained stable postbaseline in adult participants. In the subset of elderly participants (≥65 years of age) from this study, a slowing of reaction time was observed starting at Week 20 and through the end of the study; however, this appeared to represent an isolated observation related to processing speed and not a broad
attentional impairment. Performance on all other cognitive tests remained stable in elderly participants in this study.

- Notably absent in the clinical studies with esketamine were respiratory depression, QT interval prolongation, development of psychotic-like symptoms or mania, interstitial or ulcerative cystitis, treatment-emergent hepatotoxicity, and clinically significant body weight gain.

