8.3.7. Adverse Events of Special Interest

Clinically relevant intervention-emergent AEs of special interest will be summarized separately, grouped in the following MedDRA based categories:

- Sedation: sedation; somnolence; altered state of consciousness; depressed level of consciousness; hypersomnia; stupor
- **Dissociation:** depersonalisation/derealisation disorder; derealisation; dissociative disorder; flashback; hallucination; hallucination, auditory; hallucination, visual; hallucination, illusion; somatic hallucination; hyperacusis; tinnitus; diplopia; vision blurred; ocular discomfort; photophobia; visual impairment; dysesthesia; oral dysesthesia; paraesthesia; paraesthesia oral; pharyngeal paraesthesia; time perception altered; daydreaming; delusional perception; feeling hot; feeling cold; feeling of body temperature change
- **Suicidality:** completed suicide; depression suicidal; intentional overdose; intentional self-injury; multiple drug overdose intentional; poisoning deliberate; self-injurious behavior; self-injurious ideation; suicidal behavior; suicidal ideation; suicide attempt; toxicity to various agents
- Suggestive of abuse potential: aggression; confusional state; decreased activity; dependence; disorientation; dissociation; dissociative disorder; dizziness; drug abuse; drug abuse; drug dependence; drug use disorder; drug detoxification; drug diversion; drug rehabilitation; drug tolerance; drug tolerance increased; drug withdrawal convulsions; drug withdrawal headache; drug withdrawal syndrome; euphoric mood; feeling abnormal; feeling drunk; feeling of relaxation; hallucination; hallucination, auditory; hallucination, gustatory; hallucination, olfactory: hallucination. synesthetic; hallucination, tactile: hallucination. visual: hallucinations, mixed; inappropriate affect; mental impairment; product tampering; psychomotor hyperactivity; psychotic disorder; rebound effect; somatic hallucination; somnolence; substance abuser; substance dependence; substance use; substance use disorder; substance-induced mood disorder; substance-induced psychotic disorder; thinking abnormal; withdrawal arrhythmia; withdrawal syndrome
- **Cystitis**: allergic cystitis; chemical cystitis; cystitis; cystitis erosive; cystitis hemorrhagic; cystitis interstitial; cystitis noninfective; cystitis ulcer active; cystitis-like symptom; pollakiuria; dysuria; micturition urgency; nocturia

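### As supplied, the SAP's 'Suggestive of abuse potential' list lacks three terms that the protocol names, so the incidence of that category may be understated

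*SAP*

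**What the plan says.** SAP 5.7.2 summarises special-interest events in six categories, one of them events suggestive of abuse potential, and leaves the content of each to an appendix: "See Appendix 8 for a list of adverse events in each category". Appendix 8 is therefore the list that a programmer would use. Protocol 9.4.4 describes the same summary but takes the categories from Protocol 8.3.7.

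The two lists for this category part at two places:

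- **Hallucination terms.** The protocol has "feeling of relaxation; hallucination; hallucination, auditory; hallucination, gustatory". The SAP has "feeling of relaxation; hallucination, auditory; hallucination, gustatory".
- **Substance terms.** The protocol has "somnolence; substance abuser; substance dependence; substance use; substance use disorder". The SAP has "somatic hallucination; somnolence; substance abuser; substance use disorder; substance-induced mood disorder; substance-induced psychotic disorder".

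SAP 6.2 (Appendix 2) is where changes to the protocol's analyses are recorded. It mentions only that time to relapse will be analysed descriptively. It says nothing about special-interest terms.

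**The concern.** One safety output has two definitions, and the narrower one is operative without being declared. Amendment 1 added abuse potential to the special-interest events, Protocol 2.3 accepts that a potential for abuse exists, and Protocol 3 makes special-interest events part of the comparative safety endpoint. SAP 5.8.7 also carries them into the subgroup summaries, so a gap in the list would spread to those tables.

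The three terms are not affected alike. *Hallucination* stays in the SAP's Dissociation list, so such an event still counts as one of special interest, only in another category. *Substance dependence* and *substance use* are in none of the six SAP categories, so an event with either term would leave the special-interest tables altogether. Protocol 2.2.3.4 and 2.3 report that abuse was not observed in the earlier trials, so even a single event of this kind would be informative.

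**Working it through.** The plan states no figure for this category, so there is none to reproduce. The check is a term-by-term comparison followed by the counting rule.

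**Inputs.** The abuse-potential lists in Protocol 8.3.7 and SAP Appendix 8, split at the semicolons. A few separators in the protocol's hallucination terms are printed as colons or full stops. They were read as semicolons or commas.

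**Comparison**

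| | Protocol 8.3.7 | SAP Appendix 8 |
|---|---|---|
| Entries | 49 | 46 |
| Distinct terms | 48 (*drug abuse* is printed twice) | 46 |
| Only in this list | *hallucination*, *substance dependence*, *substance use* | *drug abuser* |

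The counts reconcile: 48 − 3 + 1 = 46. *Drug abuser* probably corresponds to the protocol's second *drug abuse*, so it need not be a deliberate addition.

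**Effect on incidence.** SAP 5.7.2 counts participants with at least one occurrence of each event. The same rule is taken to apply to a category. A participant then drops out of the category only if both conditions hold:

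1. the participant has at least one of the three omitted terms; and
2. the participant has none of the 46 retained terms.

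Let k be the number of such participants in an arm and N the arm's safety set. The understatement in that arm is k/N. It cannot be negative, because removing terms cannot add participants. The documents give neither k nor a rate for these terms. With N = 311 per arm assumed from the planned sample size:

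- k = 0: 0/311 = 0, no change
- k = 1: 1/311 = 0.32 percentage points
- k = 3: 3/311 = 0.96 percentage points

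**After the fix.** Restoring the terms gives 46 + 3 = 49 distinct terms, which cover all 48 in the protocol plus *drug abuser*.

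**The case against.** **The gap may be a loss in reading the PDF.** Both omissions sit where a word repeats, and the supplied text loses words in such places elsewhere. In SAP 1.2 (esketamine arm) the food and fluid restrictions run together between two mentions of the nasal spray, where the protocol synopsis has two full sentences. In the synopsis's description of the repeated-measures model the older age stratum is missing, though Protocol 9.4.2 gives it. Against this, similar pairs in Appendix 8 survive, including plain *hallucination* followed by its auditory form under Dissociation, *drug abuse* followed by *drug abuser*, and *drug tolerance* followed by *drug tolerance increased*. The objection stands as a reason to open the original SAP first. It does not settle the matter.

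**The effect may be nil.** This stands. The retained terms include dizziness, somnolence and dissociation. Protocol 2.2.3.4 lists dissociation and dizziness among the most common reactions to esketamine, and Protocol 2.2.4 lists somnolence and dizziness for quetiapine. A participant with a dropped term may well be in the category already.

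**The events are not lost.** This also stands. SAP 5.7.2 tabulates all treatment-emergent events by arm, and also by severity and by relationship. Protocol Appendix 5 separately requires suspected abuse or misuse of a sponsor study intervention to be recorded. The SAP category keeps several close terms, such as *drug dependence*, *drug use disorder* and *substance use disorder*.

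**A related inference about cystitis.** A reader might also infer that the cystitis list is faulty, because it prints "cystitis noninfective; cystitis ulcer active; cystitis-like symptom" rather than a plain entry for ulcerative cystitis. The documents do not support this. Both print the same entry, and calling it wrong would need the coding dictionary, which is not supplied. Protocol 2.2.3.4 mentions "interstitial or ulcerative cystitis, treatment-emergent hepatotoxicity" among events that were absent from earlier studies, not as a named risk.

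**Conclusion.** In the text as supplied, three protocol terms are missing from the operative SAP list and the change is undeclared. The supportable conclusion is that the incidence of this category may be understated by k/N in an arm, with k unknown and possibly 0. At k = 1 that is 0.32 percentage points, assuming 311 participants in the arm's safety set and participant-level counting for the category.

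A reader might infer that the reported incidence will be too low, or that dependence and use events will go unreported. Neither follows. The first needs at least one participant with a dropped term and no retained term, and the documents give no rate for this. The second overlooks the general adverse event tables.

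The category is descriptive and SAP 5.7.2 attaches no test to it. The primary and key secondary analyses are untouched. The point is an alignment of two definitions. It is worth making because abuse potential is a declared safety interest and the remedy costs almost nothing. It depends on the terms being absent from the original SAP.

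**What to change.** 1. Open the original SAP and read Appendix 8 against Protocol 8.3.7. If the three terms are there, nothing needs to change.
2. If they are absent, restore *hallucination*, *substance dependence* and *substance use* to the abuse-potential category. If the narrower list is intended, record and justify it in SAP 6.2 instead.
3. Do this before the special-interest tables and their subgroup versions are produced.

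The cost is a few words in the SAP and a small edit to the programmed term list. No further data are needed. Restoring the terms can only raise the reported incidence or leave it unchanged.
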